2.3.2 Known Potential Benefits

[There may not be any direct benefit to all patients. However, given the clinical data, it is likely that many participants may receive a reduction of symptoms.]

2.3.3 Assessment of Potential Risks and Benefits

[The risks associated with this study are no greater than those encountered in standard clinical treatment with Transcranial Magnetic Stimulation (TMS). The aspects of this study that are implemented for the purposes of the study alone (the MRI scan and assessments of symptoms) are minimal risk. Participants who have an obvious contraindication to TMS or MRI in their medical record will not be presented in this study; those who consent will be asked to complete an MR-safety form upon consent. Should any MRI contraindications be discovered at this time, they will not be enrolled in the study.

The potential benefit to patients (e.g., reduced time burden) and medical community through the increased understanding of this treatment method for individuals with depression, far outweighs the potential risk from the MRI and TMS procedures.]

[MagPro X100 Stimulator, Cool-B65 Butterfly Coil]

Page 15 of 39

3 STUDY OBJECTIVES AND ENDPOINTS

OBJECTIVES	ENDPOINTS	JUSTIFICATION FOR ENDPOINTS
Primary		
The primary objective is to assess clinical efficacy of HDS-TBS.	The primary outcome will be response to TMS treatment as evidenced by change in the Montgomery Asberg Depression from the pre-treatment baseline to the end of the 5-day treatment course.	We have used the MADRS in many prior studies. The MADRS will be the primary outcome measure of current depression severity as this scale was designed to be sensitive to change.
Secondary		
The secondary objective(s) are to determine the effect of iTBS on DLPFC rfMRI and establish a relationship between change in brain resting state functional connectivity and treatment effects.	To assess the effect of active HDS-TBS on the functional connectome, we will test for differences in DLPFC-SGACC connectivity between the active- treated and sham-treated after 5 days of treatment.	We will examine the connectivity between DLPFC-SGACC, using the DLPFC stimulation site, identified on neuronavigation and an a priori defined SGACC ROI.
Tertiary		
N/A	N/A	N/A

[MagPro X100 Stimulator, Cool-B65 Butterfly Coil]

Page 16 of 39

4 STUDY PLAN

4.1 Study Design

[Hypothesis 1: The null hypothesis is that there will be no difference in reductions in depressive symptoms by the end of the five-day treatment period. The alternative hypothesis is that, compared with sham, active TMS will result in a greater reduction in depressive symptoms by the end of the treatment period.

Hypothesis 2: The null hypothesis is that there will be no difference in the change in correlation from pretreatment to post-treatment between the active and sham groups. The alternative hypothesis is that, compared with sham, active TMS will result in a greater increase in correlation of the dorsal lateral prefrontal cortex (DLPFC) with limbic regions, in particular with the subgenual cingulate cortex (SGACC). This is a superiority comparison, for active relative to sham.

Participants will be recruited and will receive the Structured interview for Diagnostic and Statistical Manual of Mental Disorders, 5th Edition (DSM-V), the Montgomery-Asberg Depression Rating Scale (MADRS), the Young Mania Rating Scale (YMRS), the Oldfield Assessment for Handedness (handedness will be included in data analysis but is not an exclusionary criterion), and screening for dementia (MMSE >24). Following informed consent, participants will receive double blind randomization to active treatment with intensive iTBS rTMS or sham treatment. Participants will have a structural MRI, diffusion tensor MRI (DTI) and functional connectivity rs-fMRI scan. Both active and sham treatment will consist of 5 days of HDS-TBS treatment. We will optimize TMS coil positioning on an individual basis as described in individualized targeting of TMS to DLPFC target. On Day 2 or 3 of treatment, patients will have option to complete an additional MRI, contingent on availability and scheduling. At the end of each 5-day treatment patients will again receive an fMRI scan (one at pretreatment and 1 at post-treatment). Participants will also receive the Scale for Suicide Ideation (SSI), Hamilton Depression Rating Scale (HAM-D), additional validated self-report questionnaires, and neurocognitive assessment at pre and post-treatment. During each day of treatment, patients will complete MADRS, SSI, and YMRS to track progress. There are options for participants to complete visits remotely as possible (such as screening). The participant will also return for a 4 week follow up visit to complete MADRS, HAM-D, SSI, and YMRS. For the pre-treatment and post-treatment sessions, patients will be given the option to complete "The Battleship Task"; this is a computer-based cognitive task which examines how well patients are able to learn a set of shapes that are hidden on a grid. See "Schedule of Activities" in Section 12.1 for more detailed breakdown of the tasks per visit.

Patients will follow the recommended treatment course as best as possible. The protocol does allow for variability in the treatment timeline contingent on patient availability, MRI availability, and other scheduling factors. In this case, we are able to accommodate the participants who can not commit for 5 consecutive days or when one of these 5 days will fall on holiday. Thus, we will be able to complete the treatment course within 7-10 days.

Treatment Assessments

Primary outcome measure-Depression severity will be measured using the clinician administered Montgomery-Asberg Depression Rating Scale (MADRS). We have used the MADRS in many prior studies. The MADRS will be the primary outcome measure of current depression severity as this scale

[MagPro X100 Stimulator, Cool-B65 Butterfly Coil]

Page 17 of 39

was designed to be sensitive to change. It consists of 10 items, each of which has severity ranges with a total range of 0-60.

Treatment with High Dose Theta-burst Stimulation Procedures

Stimulation Parameters: Each participant's resting motor threshold will be determined using EMG recordings and the adaptive parameter estimation by sequential testing (PEST) algorithm, to ensure accuracy and reproducibility. Treatment sessions: iTBS will be delivered at the individually targeted DLPFC site at 90% RMT. The stimulation pattern and total number of pulses will be triplet 50 Hz bursts, repeated at intervals of 200 ms (5 Hz); 2 s on and 8 s off; 1800 pulses per session; total duration of 10 min [6]. There will be ten iTBS stimulation sessions/day on 5 sequential days. Stimulation will be double-blinded. Neuroimaging sessions will be conducted prior to iTBS treatment ('pre') and ideally 24 hours following day 5 of treatment ('post').

Sham iTBS. For both active and sham iTBS, we will use the Magventure Cool B65 A/P coil. The sham treatment works by blocking the magnetic field with an internal spacer on the sham side, allowing the operator to place the appropriate coil surface (active vs. sham) against the scalp. During the sham iTBS, we will use the coil's electric stimulation functionality that allows for the delivery of a brief electric pulse to the scalp simultaneous to the TMS pulse to mimic the scalp sensation during the sham condition. Importantly, the electric pulse is calibrated to the stimulator output to ensure a realistic sham condition. Blinding Procedures: will be implemented to control for expectancy effects related to TMS stimulation. Persons who will be blind to TMS status are patients and all study staff with the exception of [name] (the study statistician) and [name] (clinical and medical monitor). Included in blinded status is the TMS operator since "active" vs "sham" delivery will be randomized and delivered in a blinded fashion (see above).

Neuronavigation. Prior to the iTBS visits, target coordinates and orientation vectors will be generated from the fMRI data and the e-field models, and loaded into the Brainsight neuronavigation system along with the subject's reconstructed T1 image. Scalp and cortical surfaces will be generated from the T1. During the visits, the subject will be co-registered to the T1 using fiducial points at the Nasion, Tragi and nose tip. TMS pulses will be delivered to the target at the optimal orientation, and the accuracy of this targeted stimulation will be monitored and tracked by the Brainsight software.

Individualized electric-field modelling to optimize stimulation for the chosen target. Cortical anatomy varies across subjects and this variability can impact the magnitude of the electric field generated by the TMS pulse at the target. For instance, cortical gyrification creates transitions between gray matter and cerebrospinal fluid, influencing the local e-field distribution in an orientation dependent manner. In addition, conductivity anisotropy in large white matter fiber bundles leads to preferential directions for current flow, further impacting the e-field generated by TMS. To account for these sources of variability, we will use the structural and diffusion data to create finite-element models of the electric field for varying coil orientations at the individualized site of stimulation and use these models to optimize the coil orientation for each subject [7].

Neuroimaging procedures.

MRI data will be acquired on a 3 Tesla Siemens Prisma scanner using a 64 channel head coil (Erlangen, Germany). Our acquisitions are optimized for Siemens Prisma scanners and are rigorously tested as part of the human connectome project (HCP). In the rs-fMRI targeting session T1-weighted, T2-weighted, and rs-fMRI (2x 8 min) scans will be collected using the 64-channel head coil.]

[MagPro X100 Stimulator, Cool-B65 Butterfly Coil]

Page 18 of 39

4.2 Scientific Rationale for Study Design

[The project is testing whether using high dose spaced theta-burst rTMS (HDS-TBS) produces a significant reduction in depressive symptoms and uses a comparison with sham.]

4.3 **Justification for Dose**

[N/A – This project does not include dosage of medication.]

4.4 End of Study Definition

[A participant is considered to have completed the study if they have completed all phases of the study shown in the Schedule of Activities (SoA), Appendix Section 12.1.]

[MagPro X100 Stimulator, Cool-B65 Butterfly Coil]

Page 19 of 39

5 STUDY POPULATION

5.1 Inclusion Criteria

[In order to be eligible to participate in this study, an individual must meet all of the following criteria:

- Bipolar depression (BP I and BP II) by DSM 5 criteria [8]
- Age 18-70
- Right or left handed
- All genders
- Treatment resistant depression, as in they must have treatment resistant depression with 2 or more prior antidepressant trials that have failed to produce a response (> 50% reduction in symptoms) using ATHF criteria [9]
- Able to provide informed consent to participate in the study
- Must be on a stable medication regimen, requiring at least one mood stabilizer
- Depression severity as represented by scoring at least 20 on MADRS

If unsure about participants' eligibility, the research team may contact the participants' treatment provider (i.e. psychologist, nurse practitioner, psychiatrist) to gather additional information to make a determination.]

5.2 Exclusion Criteria

[An individual who meets any of the following criteria will be excluded from participation in this study:

- No current substance abuse disorder for the past 6 months (previous substance abuse not exclusionary)
- Any psychotic disorder or current active psychotic symptoms (personality disorders not exclusionary unless in the opinion of the referring psychiatrist it would jeopardize participation)
- No dementia or other major neurological disorders
- Not having depression as primary disorder
- No major medical illness, for example metastatic cancer, end stage renal disease
- Not able to verify contact information. Participants must be able to follow through with the study & must have verified contact information and at least one verified contact
- Pregnancy. While there are no known risks to a fetus this is a new use of TMS, which has not been tested, thus pregnancy is exclusionary
- Score on YMRS greater than 12 (patients with mixed features have been shown not to respond well to TMS treatment [10])
- Rapid cycling Bipolar illness (patients with > 4 mood episodes within the past year will be excluded, as they have a higher risk of switch to mania [11])

[MagPro X100 Stimulator, Cool-B65 Butterfly Coil]

Page 20 of 39

- Any implants, conditions, or contraindications that would be deemed unsafe for TMS or MRI
- Currently using benzodiazepines (such as lorazepam) with a dose >1 mg per day or equivalent]

5.3 Lifestyle Considerations

[Patients will not be asked to discontinue their outside treatment. There is no evidence suggesting that compounding treatments may worsen depressive symptoms.]

5.4 Screen Failures

[Screen failures are defined as participants who consent to participate in the clinical trial but are found to be ineligible during or after screening. A minimal set of screen failure information is required to ensure transparent reporting of screen failure participants. Minimal information may include: demography, screen failure details, eligibility criteria, and any serious adverse event (SAE).

Individuals who do not meet the criteria for participation in this trial (screen failure) because of current depressive symptoms or treatments may be rescreened. Rescreened participants should be assigned the same participant number as for the initial screening.]

5.5 Strategies for Recruitment and Retention

[All participants will be recruited through the University of Pennsylvania resources and the surrounding community.

Patients can express interest by initiating contact with the research staff for a center wide phone or self-report screening. Responses will be stored in REDCap and reviewed by study coordinators. Patients who meet inclusion and exclusion criteria will be invited to the screening visit.

All recruitment materials, including but not limited to self-report screening, phone screening, flyers, brochures, referral letters, online postings, and email templates will be IRB-approved before distribution.]

[MagPro X100 Stimulator, Cool-B65 Butterfly Coil]

Page 21 of 39

6 STUDY INTERVENTION

6.1 Study Intervention(s) Administration

6.1.1 Study Intervention Description

Name of Device	Manufacturer	Marketing Status in the U.S.	FDA Device Classification (I, II, III)
MagPro X100	MagVenture	FDA approved	II
Cool-B65 A/P	MagVenture	FDA approved	II

6.1.2 Dosing and Administration

[Prior to beginning treatment, participants will undergo resting motor threshold (RMT) to determine the level of ideal for the stimulation sessions. During treatment (day 1-5), iTBS will be delivered at the individually targeted DLPFC site at 90% RMT. The stimulation pattern and total number of pulses will be triplet 50 Hz bursts, repeated at intervals of 200 ms (5 Hz); 2 s on and 8 s off; 1800 pulses per session; total duration of 10 min [6]. There will be ten iTBS stimulation sessions/day on 5 sequential days.]

6.2 Preparation/Handling/Storage/Accountability

6.2.1 Acquisition and accountability

[All interventional devices are owned, stored, and managed by the Center for Neuromodulation in Depression and Stress (CNDS).]

6.2.2 Formulation, Appearance, Packaging, and Labeling

[Devices are already owned and set up by the CNDS. Trained staff will check and prepare the devices as needed throughout the study.]

6.2.3 Product Storage and Stability

[All devices are stored behind locked doors with access restricted to members of the CNDS. These devices are located in the CNDS lab-space in the Richards Biomedical Building. Devices are stored and set up as per manufacturer requirements/recommendations.]

6.2.4 Preparation

[Devices are already set up in the CNDS lab-space.

Prior to the iTBS visits, target coordinates and orientation vectors will be generated from the fMRI data and the e-field models, and loaded into the Brainsight neuronavigation system along

[MagPro X100 Stimulator, Cool-B65 Butterfly Coil]

Page 22 of 39

with the subject's reconstructed T1 image. Scalp and cortical surfaces will be generated from the T1. During the visits, the subject will be co-registered to the T1 using fiducial points at the Nasion, Tragi and nose tip. TMS pulses will be delivered to the target at the optimal orientation, and the accuracy of this targeted stimulation will be monitored and tracked by the Brainsight software.

Motor threshold will be determined prior to TMS administration. Throughout the course of the treatment, trained staff will check the machine before use and set the machine to the necessary parameters.]

6.3 Measures to Minimize Bias: Randomization and Blinding

[Patients who are enrolled in the study (i.e., met inclusion/exclusion criteria) will be randomized to active TMS or Sham by a randomization system determined by the Independent Randomization Provider (IRP). This will occur at least one day before the start of treatment.

Only trained staff will administer the TMS treatment and the required clinical assessments during the study visits. These staff (as well as the PI and the patients) will also be blinded until the end of the study. Included in blinded status is the TMS operator since "active" vs "sham" delivery will be randomized and delivered in a blinded fashion. The only exception will be [name] (the study statistician) and [name] (clinical and medical monitor).]

6.4 Study Intervention Compliance

[Trained staff will administer TMS and monitor patients throughout treatment. They will use an SOP to ensure study compliance, including tracking the necessary TMS sessions. [name] will act as clinical and medical monitor to ensure intervention compliance.]

6.5 Concomitant Therapy

[For this protocol, patients may have an existing treatment regimen outside of the trial (i.e., antidepressant medication or mood stabilizers). Prior to enrolling, patients will be asked about any outside treatments and must have been enrolled in their treatment for at least 4 weeks prior to completing the baseline for this trial. This will be confirmed during screening visits as well. Patients will be asked to continue their same treatments during study participation.]

6.5.1 Rescue Medicine

[N/A - This study will not supply rescue medication.]

[MagPro X100 Stimulator, Cool-B65 Butterfly Coil]

Page 23 of 39

7 STUDY INTERVENTION DISCONTINUATION AND PARTICIPANT DISCONTINUATION/WITHDRAWAL

7.1 Discontinuation of Study Intervention

[N/A – Patients are not able to remain in the trial without enrolling in the treatment. Discontinuation from the TMS will mean discontinuation from the study. Ending TMS due to AE will be documented and patient will be evaluated for safety.]

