7.2 Participant Discontinuation/Withdrawal from the Study

[Participants are free to withdraw from participation in the study at any time upon request. The PI may discontinue or withdraw a participant from the study for the following reasons:

• Participants may be withdrawn from the study by staff if deemed necessary for their health or safety.

We anticipate that some participants may withdraw. We do not expect early termination of participation due to patient or investigator withdrawal to have any impact on safety or well-being of participants. Patients who withdraw for AE will be evaluated by trained staff for safety.

Participants who enroll in the study (i.e., sign consent and pass screening) and are subsequently withdrawn will be replaced.]

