8.2 Safety and Other Assessments

[Participants will complete the following in order to determine their eligibility for the project: Structured interview for Diagnostic and Statistical Manual of Mental Disorders 5th Edition (DSM-V), the Montgomery-Asberg Depression Rating Scale (MADRS), the Young Mania Rating Scale (YMRS), the Oldfield Assessment for Handedness (handedness will be included in data analysis but is not an exclusionary criterion), and screening for dementia (MMSE >24).

In addition, patients will complete safety screening for both the MRI scan and the TMS administration, screening out individuals who may not be able to complete these tasks.

[MagPro X100 Stimulator, Cool-B65 Butterfly Coil]

Page 25 of 39

Throughout treatment, patients will be monitored by certified personnel. MADRS will be completed during each day of TMS treatment, which will allow staff to monitor symptom severity for safety as well. Any safety concerns will be brought to the PI and necessary personnel.]

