9.3 Populations for Analyses

[The analyses will follow the Intention-to-Treat principle, with all randomized participants contributing to analyses. In particular, the linear mixed effects models to be used for the primary hypothesis will make use of all data, partial or complete, provided by the participants.]

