9.4.2 Analysis of the Primary Efficacy Endpoint(s)

[Aim 1: To assess clinical efficacy of HDS-TBS.

Hypothesis 1: Compared with sham, active TMS will result in a greater reduction in depressive symptoms by the end of the treatment period. Each patient will receive either one five day sham or one 5-day active treatment.

The primary outcome will be based on the set of repeated Montgomery Asberg Depression scores obtained at baseline and on each of the five treatment days. We will use linear mixed effects models to compare the two treatment groups on change from baseline across the five days. As noted above, the response may be transformed to reduce levels of skewness. The main fixed effects will be the treatment group indicator, and we expect that a random intercept will accommodate the within person correlations over the five daily measures of change.

Power for Hypothesis 1: We use the methods of Hedeker, Gibbons and Waternaux [13]. For a random intercept model with correlation coefficient of rho=0.3, we have 80% power for a group effect of Cohen's d=0.72.

Estimated regression coefficients will be reported, along with standard errors, associated confidence intervals, and p-values for hypothesis tests. In analyses adjusting for covariates, adjusted least squares means for treatment groups will be reported.

Little missing data is expected for the baseline and five-day treatment period. The mixed effects models used for Hypothesis 1 will use any data, partial or complete, provided by the randomized participants, and will yield valid estimates under missing-at-random assumptions.]

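### Stopping TMS ends MADRS collection, so the remaining scores rest on missing-at-random with no sensitivity analysis; the likely effect is modest and cheap to reduce

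*Combined protocol and SAP*

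**What the plan says.** Section 7.1: "Discontinuation from the TMS will mean discontinuation from the study". For a stop due to an adverse event, it provides only for documentation and a safety evaluation.

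Section 7.2 foresees some withdrawals, at the participant's request or by staff: "Participants may be withdrawn from the study by staff if deemed necessary for their health or safety". It also says that withdrawn participants will be replaced.

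The schedule in 12.1 places MADRS at screening, on the five TMS session days, at the post-stimulation visit and at four weeks. It has no early-termination visit. That no MADRS is taken after a stop is therefore an inference from 7.1 and 12.1, but nothing elsewhere provides for one.

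Section 9.3 adopts Intention-to-Treat and says that the primary mixed models "will make use of all data, partial or complete, provided by the participants". Section 9.4.2 will "compare the two treatment groups on change from baseline across the five days" and states that the models "will yield valid estimates under missing-at-random assumptions". Sections 9.4.1 and 9.4.2 expect little missing data. The only extra analyses that 9.4.1 specifies add imbalanced covariates, and 9.4.9 leaves room for unspecified later ones. None addresses missing scores.

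On the timing of randomization, 6.3 says: "This will occur at least one day before the start of treatment".

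**The concern.** The scores go missing because of a protocol rule, not only because patients decline. A stopper's remaining daily scores are then supplied implicitly by the model.

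Missing-at-random is reasonable when the recorded MADRS explains the stop. That will cover some cases, since 8.2 says "MADRS will be completed during each day of TMS treatment, which will allow staff to monitor symptom severity for safety as well". It is less secure when someone stops for an adverse event or a safety reason that earlier MADRS scores do not reflect. If such stops differ between arms and go with worse (or better) unseen scores, the treatment contrast is biased. With no sensitivity analysis, a reader could not tell by how much.

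There is also a gap before treatment. Randomization precedes Day 1 by at least a day, and the next scheduled MADRS is on Day 1. Someone who leaves in between has no post-randomization score and gives the group comparison little or no information.

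**Working it through.** **Inputs from the documents.** 34 subjects with 32 usable (1.1); five daily changes from baseline, random intercept (9.4.2); rho = 0.3 and 80% power at d = 0.72 (9.2).

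**Assumptions.** 1:1 allocation, two-sided 5% z test, compound symmetry, marginal SD 1. Stop numbers, timing, arm split and the size of the unseen shift are also assumed, because the documents give none of them.

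**The plan's own figure.** The variance of a five-day mean is (1 + 4 × 0.3)/5 = 0.44.
- 16 per arm: SE = √(0.44 × 2/16) = 0.2345; power = Φ(0.72/0.2345 − 1.96) = 86.7%.
- 17 per arm: SE = √(0.44 × 2/17) = 0.2275; power = 88.6%.

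The stated 80% is not reproduced; 14 per arm would give 81.9%. The mismatch is on the cautious side and this point does not depend on it.

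**Bias from unseen scores.** Let m of n participants in one arm stop after k observed days, with true scores on the other 5 − k days worse by delta than missing-at-random predicts. In a model with day effects and one group effect:

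bias in the five-day average = (m/n) × ((5 − k)/5) × delta.

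This does not depend on rho. Example: m = 2, n = 17, k = 1, delta = 1 SD gives (2/17) × (4/5) × 1 = 0.094 SD.

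The SE comes from generalized least squares with those days missing. Rejection is the chance that |Z| exceeds 1.96 when Z has mean bias/SE and the true five-day contrast is zero.

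| Two stops in one arm, after | Bias, 1 SD | SE | Bias/SE | Rejection, 1 SD | Rejection, 2 SD |
|---|---|---|---|---|---|
| Day 4 | 0.024 | 0.228 | 0.1 | 5.1% | 5.5% |
| Day 3 | 0.047 | 0.229 | 0.2 | 5.5% | 7.0% |
| Day 2 | 0.071 | 0.230 | 0.3 | 6.1% | 9.4% |
| Day 1 | 0.094 | 0.232 | 0.4 | 6.9% | 12.8% |
| no treatment day | 0.118 | 0.235 | 0.5 | 7.9% | 17.0% |

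- Bias doubles at 2 SD. From 0.024 to 0.094 SD is 3% to 13% of d = 0.72.
- One stop gives half the bias. One per arm with the same timing and shift gives zero. Stops in the other arm reverse the sign.
- If both are replaced in the same arm and kept in the analysis (19 against 17), the factor 2/17 becomes 2/19. The bias is then about 11% smaller: 0.021 to 0.084 SD for stops after Days 4 to 1.
- Higher correlation raises the SE and lowers rejection. For stops after Day 1, rejection at 1 and 2 SD is 6.4% and 10.8% at rho = 0.5, and 6.1% and 9.6% at rho = 0.7.
- For a Day-5 contrast, which is closer to the wording of Hypothesis 1, every stop before Day 5 counts in full: (2/17) × 1 = 0.12 SD, whichever day it occurs.

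**The case against.** The strongest reply is that the effect is small. The synopsis allows about two losses over both arms, for any reason and possibly including imaging losses. Putting two stops in one arm uses the whole allowance in the least favourable split, and the rejection rates above 7.9% need a 2 SD shift. The course is short. Missed days are not stops either: 7.3 has staff reschedule missed visits, and 4.1 says "we will be able to complete the treatment course within 7-10 days". The missing-at-random assumption is stated openly. All of this stands. It makes the point modest, but it does not explain why ratings should cease when TMS does.

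Four stronger readings are tempting, and the documents do not support them:
- **That 7.1 contradicts the Intention-to-Treat statement.** Section 9.3 promises use of the data that participants provide, and scores before a stop are kept.
- **That someone leaving before Day 1 adds nothing, despite 9.3.** This depends on the model. If only change scores are responses, that person has none. If baseline is itself a response, as 9.4.1 may imply, the person enters the model with little information on the group difference.
- **That the result is biased in favour of active treatment.** Direction depends on which arm loses participants and why, and neither is known.
- **That continued ratings would recover most of the lost scores.** The documents do not say how many stops would be consent withdrawals, for which ratings would also end.

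**Conclusion.** The point holds as a cheap improvement. The stop rule in 7.1, with no post-stop rating in 12.1, leaves the remaining scores uncollected, and the primary analysis relies on missing-at-random for them with no planned check. If stops are few, as the synopsis suggests, the likely bias is well below one standard error: 0.02 to 0.09 SD in the unfavourable two-in-one-arm case at 1 SD, and less or zero in milder ones. A Day-5 contrast would be somewhat more exposed, at 0.12 SD. Loss of precision is negligible (SE 0.228 with complete data, at most 0.235). The shift, timing and arm split are illustrative. What is certain is that the rule discards ratings already in the schedule and leaves the reader no means to judge the consequence.

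**What to change.** 1. Amend 7.1 so that stopping TMS does not by itself end outcome collection. Unless consent is withdrawn, take the remaining daily MADRS ratings on the participant's remaining session dates as scheduled at the time of the stop, remotely where possible. For someone who leaves before Day 1, use the scheduled Days 1 to 5. Include these scores in the primary model in the randomized arm. Using the schedule current at the stop matters because a course may run over 7 to 10 days: dates fixed at randomization could already have passed, and would put stoppers and completers on different time scales.
2. Keep the post-stimulation and four-week MADRS, YMRS and SSI for these participants, for secondary and safety summaries.
3. Add one sensitivity analysis that shifts unobserved post-stop scores by a stated range, for example 0.5 to 2 SD worse, in each arm in turn.

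The clinical decision to stop TMS is unchanged. The cost is a short amendment, a few extra rating contacts with scales already in use, and one extra analysis. Some stoppers will decline, so some scores will still be missing, which is why item 3 is needed as well as item 1.
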